1.0 Objectives / Specific Aims

Normal aging is characterized by changes in the immune system that result in increased susceptibility to infections, poor response to new vaccine antigens, loss of protection offered by previous vaccinations and decreased immune surveillance [1, 2]. Despite the chronic inflammation associated with immunosenescence, the aging population is living longer. Consequently, individuals >65 years of age, are the most rapidly growing population amongst those with end stage renal disease (ESRD) and account for more than 18% of renal transplant (RT) recipients [3].

The incidence of pneumococcal disease is significantly higher in both elderly [4] and those with RT [5] and the combination of these factors is likely additive, if not synergistic, for invasive pneumococcal disease (IPD). It is recommended that both elderly >65 and RT recipients be vaccinated with a regimen that includes both the 13-valent pneumococcal conjugate vaccine (PCV13) and the 23-valent pneumococcal polysaccharide vaccine (PPV23). However, small immunogenicity studies performed in the transplant populations have not shown superiority of a PCV containing regimen [6, 7]. Moreover, the addition of PCV to the pneumococcal vaccine regimen does not improve protective immunity in this population. Studies to date fail to elucidate the possible foundation of the disappointing immune responses to the PCV regimens, data essential for the development of a rational and effective next generation pneumococcal vaccine.

Specific Aim 1.

We will **define immune responses by measuring** serum antibody and functional antibody responses to PPS 14, 19A and 23F following PCV13 vaccination in RT recipients 65-75 years of age and compare these to: RT recipients 35-45 years of age and persons with DM/HTN but normal function 65-75 years of age to dissect out the age and RT components respectively. Healthy persons 35-45 and 65-75 years of age will be studied as age appropriate reference.

Specific Aim 2.

We will measure and characterize the antigen-specific B cell subset response following immunization with PCV13 in the RT recipients 65-75 years of age and compare them to each of the groups described in Specific Aim 1 using flow cytometry and fluorescently labeled PPS and monoclonal antibodies. These measures will be correlated with post-immunization functional antibody activity, a surrogate of protection.

Specific Aim 3.

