5.0 Inclusion and Exclusion Criteria/ Study Population

Age ranges were chosen based on previous published and unpublished studies performed in our laboratory indicating that a significant decrease in pneumococcal vaccine response starts to appear at age 65 and that prior to age 50 the response is similar to individuals 20-30 age of years, i.e. optimal range. We chose the 35-45 age group specifically, and not 20-30, as renal transplants recipients with cause of renal failure is type II diabetes or hypertension are well represented in the MUSC transplant population.

Individuals will be screened for eligibility depending on the group they are recruited for:

Group 1 Older RT group (Age 65-75)

Group 2 Younger RT group (Age 35-45)

The elderly (65-75 years) and young (35-45 years) renal transplant recipient groups 1 and 2 seen at the MUSC and VA transplant clinics whose end-stage renal disease was caused by hypertension (HTN) and/or DM II who are at least 1 year post-transplant and due for their PCV 13 vaccination will be asked to participate in the study. Those that do not wish to participate in the study will receive the clinical standard of care.

Group 3 Individuals with DM II and/or HTN age 65-75.

Individuals with the diagnosis DM II and/or HTN due for routine visits at the general internal medicine or endocrinology clinic at the Ralph H Johnson VA Medical Center will be screened for normal (Glomerular filtration rate \geq 60) versus abnormal (GFR $<$ 60) who are due for their standard of care PCV13 vaccine will be asked to participate.

Group 4: 65-75 years old without DM2 or renal impairment who are due for their standard of care vaccination with PCV13.

Group 5: Healthy persons 35-45 years of age without DM or renal impairment willing to participate in a study to receive PPV23, if they have not received this previously or/and PCV13, at least 1 year after PPV23 vaccination.

Inclusion/Exclusion criteria

Inclusion criteria are group specific. HBV, HCV and HIV testing are not necessary in the RT groups as all RT recipients are tested prior to transplant.

Exclusion criteria are either applicable to all groups or group specific. Therefore we have listed the exclusion criteria applicable to ALL groups first. Group specific criteria are listed under each group

Exclusion Criteria common to all groups

1. Previous immunization with PCV13.

2. Pregnancy, no contraceptive practice in women of childbearing age, or breastfeeding

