3. Known anaphylaxis, hypersensitivity or “bad allergic reaction” to the pneumonia vaccine. This does not include egg allergy or previous Guillan Barre syndrome.
4. Those who received blood products or gamma globulin within 3 months.
5. Inability to comprehend or sign the informed consent form
7. Previous/present illness that may affect immune response to the vaccine (previous pneumococcal Disease, removal of the spleen, auto-immune disease such as lupus or rheumatoid arthritis, end-stage liver disease, or cancer)
8. Significant abnormalities (3xULN and all those considered to be critical values) in CBC, chemistries including glucose.
9. HIV, HBsAg or HCV positivity
10. Receipt of PPV23 within 1 year

Groups 1 (65-75 yrs) and 2 (35-45 yrs) Renal Transplant populations

Inclusion Criteria:

Age range; RT 35-45 or 65-75 years old,
 End stage renal disease cause either DM2 and/or hypertension (HTN)
 Renal transplant >12 months ago
 We will not restrict volunteers with respect to gender, ethnic or racial group.

Exclusion criteria:

1. Medications that are known to affect immune function (chemotherapy, anti-TNF α agents) with the exception of anti-rejection medication.
 2. Episode of acute rejection within the last 6 month period
- The inclusion/exclusion criteria will be determined by chart review and pregnancy test for females of child bearing potential.

Group 3: Diabetic/hypertensive 65-75 year old controls

Inclusion Criteria

65-75 years old with DM2 and/or HTN.
 Previous immunization with PPV23 >1 year prior
 Willingness to be tested for HIV, HBV and HCV
 “normal kidney function” defined as glomerular filtration rate (GFR) of 60% or above
 We will not restrict volunteers with respect to gender, ethnic, or racial group.

Exclusion Criteria

1. Medications that are known to affect immune function (chemotherapy, anti-TNF α agents).

The inclusion/exclusion criteria will be determined by chart review.

Group 4: Healthy Control 65-75 yr old

Inclusion Criteria

65-75 years old without DM2. May have high blood pressure (systolic>140 and/or diastolic>90) as long as it is well controlled (systolic<140 and/or diastolic <90) and has not affected kidney function.
 Previous receipt of PPV23 > 1 year prior
 Willingness to be tested for HIV, HBV and HCV
 We will not restrict volunteers with respect to gender, ethnic, or racial group.

Exclusion Criteria

6. Medications that are known to affect immune function (chemotherapy, anti-TNF α agents).

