10.0 Study Design / Methods

The overall objective of this proposal is to characterize the immune response and explore possible mechanisms of poor vaccine responsiveness following immunization with PCV in the rapidly growing group of elderly with RT. As the RT population is a heterogeneous group we will study only those in whom the underlying cause of renal failure is diabetes mellitus type 2 (DM2) and/or hypertension (HTN). There will be 5 study groups as outlined above.

Volunteers from all 5 study groups will be recruited as above. All individuals from study groups 1-4 who meet the study criteria will receive Prevnar13[®] on day 0. Group 5 volunteers will be recruited during the first year of the study and those who have not previously received PPV23 will receive PPV23 on day 0 and PCV13 on day 366. Blood samples will be obtained as outlined below and results obtained in various groups will be compared.

Timing of blood samples

Peripheral blood samples will be collected at day 0 (pre-immune), day 7, and day 30 (4 weeks post-PPV23) for groups 1-4 and at days 366, 373 and 396 for group 5. In addition, day 5, and 10 blood samples will be obtained from a limited (n=10) number of elderly RT participants to determine the optimal time point for circulation of PPS-specific B cells. Yearly blood samples will be obtained thereafter for serum antibody and OPA analyses to test longevity of antibody and OPA responses. Samples from days 0, 30 and yearly samples will be used for antibody titers and opsonophagocytic assays. Samples from day 0 (day of vaccination with PCV13) and day 7 will be used for flow cytometric analysis. The day 7 time point for isolation of antigen-specific B cells was specifically chosen as we have extensively studied temporal dynamics of antigen-specific B cell in peripheral blood samples (unpublished studies) and have found that the highest number of antigen-specific B cells are present in the peripheral circulation at day 6 and 7 with rapid (70+%) decline at day 8 in healthy young, elderly including those with DM2 and HTN, and HIV-positive. At day 30, a minimal number of PPS-specific B cells were present. Others have described similar findings [28, 29].

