The vaccine(s) administered to the participants are FDA approved vaccinations and vaccination protocols. The standard and recommended dose of vaccine will be administered either by a qualified nurse or physician and both vaccines are considered low risk. In groups 1-4 PCV13 will be administered per standard of care and is not part of the experimental protocol. In group 5, both PPV23 and PCV 13 are not routine part of care and are part of the experimental protocol. These vaccines have however been extensively studied in this and other populations and are considered low risk and 70-80% protective against pneumococcal disease [30].

The risk associated with blood draws is minimal.

The data to be collected will be stored using an excel spread sheet. The data include:

-cause of end stage kidney disease if applicable

Date of kidney transplant

Complete blood count (CBC), comprehensive chemistry profile including renal and liver functions, HbA1c, serum albumin as measure of nutrition, HbsAg, HCV and HIV test

Pre- and post-immunization serum antibody titers and opsonophagocytic antibody titers to PPS14, 19A and 23F in ug/mL

IgM and switched memory B cell number and percentage

PPS+ B cell number and percentage

Serum BAFF concentration

Gene expression of the genes listed below in Table 4

#	GENE SYMBOL	GENE TITLE	PROTEIN FUNCTION	#	GENE SYMBOL	GENE TITLE	PROTEIN FUNCTION
Apoptosis				Lymphocyte signaling			
1	Bcl-2	B-cell lymphoma 2	Apoptotic suppressor	30	CBLB	E3 ubiquitin-protein ligase	Negatively regulates B cell Ag receptor signaling
2	Bcl-Xl (BCL1)	B-cell lymphoma-extra large	Apoptotic suppressor	31	FCRL2	Fc receptor like 2	Expressed in memory B cells in humans
3	Mcl-1	Induced myeloid leukemia cell differentiation protein Mcl-1	Apoptotic suppressor	32	CD1D	CD1D	Antigen presentation
4	BAX	BCL2-associated X protein	Pro-apoptotic function	33	CD200	OX2 membrane glycoprotein	Controls inflammation; immunosuppression
5	BAD	BCL2-associated agonist of cell death	Pro-apoptotic function	34	LAIR1	Leukocyte associated immunoglobulin like receptor 1	Inhibitor of B cell mediated signaling
6	BIM (BCL11)	BCL2-interacting mediator of cell death	Pro-apoptotic function	35	CD72	B cell differentiation antigen CD72	Negative regulator of B cell responsiveness
7	FAS	Fas cell surface death receptor	Apoptosis signaling	36	RFTN1	Raft linking protein	B cell antigen receptor mediated signaling

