12.0 Data Management

Statistical Analysis Plan and Sample Size Justification for Aims 1 and 2

The primary outcomes in Aim 1 are serum antibody levels and functional antibody response measured using the OPA response at baseline and 30 days post-PVC₁₃ vaccine measured in the five groups defined in Table 1. The primary outcomes in Aim 2 are absolute number and proportion of B-cells phenotype specific to PPS₁₄, 19A, and 23F at baseline and 7 days post-PVC₁₃ vaccine measured in the same five groups. Comparisons between groups and within group between times for each aim will be evaluated using a linear

mixed model (LMM) approach. **The models will include fixed effects for participant group (65-75 RT, 35-45 RT, 65-75 DM/HTN, 65-75 healthy, and 35-45 healthy) and for time (day 0 or 30) and a random subject effect to account for repeated measures of antibody levels within participant.** Model assumptions will be checked graphically and transformations will be considered when necessary. Comparisons for each outcome between groups and within group between times will be evaluated using a series of contrasts from the LMM. **We are presenting power calculations for a range of assumptions to demonstrate that we anticipate having sufficient power to detect observed differences for all comparisons even if we fail to meet the recruitment target.** For power calculations we estimated the effect sizes for sample sizes ranging between 10 to 40 participants per group measured at 2 times at 80% and 90% power using a two-sided test assuming within subject correlation of 0.5 and Bonferroni adjusted and unadjusted significance

Figure 7: Effect sizes for different sample sizes, power, and significance

levels of $p = 0.005$ and 0.05 respectively. We will also evaluate the correlation between serum antibody levels and B cell count with OPA response across all participant groups using an LMM approach where OPA response is the dependent variable and antibody level or B-cell count is the independent variable. The model will include a random subject effect to account for repeated measures in the same subject. We anticipate good correlation (between 0.6-0.99), thus the objective is to estimate the correlation and define the level of precision around that correlation. A sample size of 200 subjects, 40 per group, provides >80% power to detect weak correlations of $r = 0.20$ and allows us to estimate a 95% confidence interval around the correlation to within ± 0.14 .

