Statistical Analysis Plan and Sample Size Justification for Aim 3

Aim 3 will examine differences in expression of TNFR markers (TACI, BCMA, and BAFF-R) using single cell qPCR on a subset of 10 participants (5 responders and 5 non-responders) from each of the 5 groups described in Aims 1 and 2 evaluated at baseline and 7 days post-vaccination. Single cell qPCR allows us to not only evaluate differences in expression between groups but also allows us to estimate the within subject and within group heterogeneity with great precision. Each participant sample provides between 40-96 viable cells that will be evaluated for gene expression at the single cell level. Relative fold-change in expression between participants who are 65-75 RT, 35-45 RT, or 65-75 DM/HTN with respect to the relevant controls will be evaluated using a linear mixed model approach. The model will include fixed effects for participant group, response status, and time and a random subject effect to account for repeated measurements resulting from individual cells from the same subject samples. Comparisons of number of gene expression between groups and within group between times will be evaluated using a series of contrasts from the LMM. For comparisons within group between responders and non-responders, a sample size of 5 responders and 5 non-responders with ≥ 40 cell level measures at 2 time points provides 80% power to detect 2.7 fold-increase or a 0.60 fold-decrease in expression using a two-sided test assuming within subject correlation of 0.5 and a Bonferroni corrected significance level (up to 10 comparisons) of $p = 0.005$. For comparisons between groups, we will have 10 subjects per group allowing us to detect even smaller fold-changes in expression.

All electronic data will be kept on the VA secure V drive or R drive and on MUSC secure Z drive that only team members will have access to.

13.0 Provisions to Monitor the Data to Ensure the Safety of Subjects (if applicable)

All adverse events (AE) will be reported and monitored through the data safety monitoring plan. The AE's will be characterized by: intensity/severity; expectedness; relatedness; frequency; outcome; treatment or action taken.

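### Diabetes share is left free to differ between Groups 1, 2 and 3 and is absent from the Aims 1-2 model, so the transplant contrast and, separately, the age contrast among recipients can be confounded by diabetes, by an unknown amount

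*Combined protocol and SAP*

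**What the plan says.** Specific Aim 1 (section 1.0) compares older recipients with younger recipients and with "persons with DM/HTN but normal function 65-75 years of age to dissect out the age and RT components respectively". Group 1 vs 2 is thus the age contrast and Group 1 vs 3 the transplant contrast.

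Section 10.0 calls the recipient population heterogeneous and gives restriction as the remedy: "we will study only those in whom the underlying cause of renal failure is diabetes mellitus type 2 (DM2) and/or hypertension (HTN"). In section 5.0 the criterion for Groups 1 and 2 is "End stage renal disease cause either DM2 and/or hypertension (HTN"), and for Group 3 it is "65-75 years old with DM2 and/or HTN". Groups 1 and 2 come from the MUSC and VA transplant clinics. Group 3 is drawn from "Individuals with the diagnosis DM II and/or HTN due for routine visits at the general internal medicine or endocrinology clinic" at the VA. The diversity paragraph of section 5.0 aims at a similar sex and race pattern across groups and does not mention diabetes.

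For Aims 1 and 2, section 12.0 states: "The models will include fixed effects for participant group (65-75 RT, 35-45 RT, 65-75 DM/HTN, 65-75 healthy, and 35-45 healthy) and for time", plus a random subject effect. For Aim 3: "The model will include fixed effects for participant group, response status, and time and a random subject effect". Neither has a diabetes term, and no diabetes subgroup or sensitivity analysis is planned. The data list in section 10.0 includes "cause of end stage kidney disease if applicable" and HbA1c, but no yes/no item for DM2.

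**The concern.** Group 1 vs 3 isolates transplant only if the two groups carry a similar burden of the underlying disease. The and/or wording is satisfied by an all-diabetic group, an all-hypertensive group, or anything between, independently in each group. With different source clinics and no tally, nothing in the plan makes the diabetes shares agree.

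The age contrast has its own version of the gap. Group 3 plays no part in it. The only control there is the restriction on cause of renal failure, and the same and/or leaves the diabetic share of Groups 1 and 2 open.

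The protocol itself separates the two conditions. Groups 4 and 5 exclude DM2 but allow controlled hypertension. A person aged 65-75 with controlled hypertension, no DM2 and normal kidney function can therefore meet the disease criteria of both Group 3 and Group 4, so Group 3 could in principle contain few diabetics.

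If diabetes alters the antibody, OPA or B-cell response and the shares differ, a difference read as transplant or age would be partly diabetes.

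**Working it through.** **The plan's own figures.** No stated figure concerns diabetes, and Figure 7 (effect sizes) is not available to check. The figures that can be checked in section 12.0 reproduce:
- Correlation, 200 subjects, r = 0.20: atanh(0.20) × √197 − 1.96 = 0.2027 × 14.036 − 1.96 = 0.885, and Φ(0.885) = 81.2% (stated: above 80%). The half-width at r = 0 is tanh(1.96/14.036) = 0.139 (stated: 0.14).
- Five groups give 10 pairwise comparisons, and 0.05/10 = 0.005, the stated adjusted level.

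Neither depends on the diabetes mix.

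**Inputs for the check**
- From section 12.0: n = 40 per group, two-sided alpha 0.05 and 0.005, within-subject correlation 0.5. With correlation 0.5, the SD of a change score is √(2(1 − 0.5)) = 1 single-time SD.
- Assumed, because the documents give neither: a share difference of 20 to 40 points and a diabetes effect of 0.2 to 0.8 SD.

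**Formulas.** Bias b = share difference × diabetes effect. SE = √(2/40) = 0.2236 SD. False-positive rate when there is no true group difference = Φ(b/SE − z) + Φ(−b/SE − z), with z = 1.960 or 2.807.

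| Share difference | Effect (SD) | b (SD) | b/SE | alpha 0.05 | alpha 0.005 |
|---|---|---|---|---|---|
| 20 points | 0.2 | 0.04 | 0.18 | 5.4% | 0.6% |
| 20 points | 0.5 | 0.10 | 0.45 | 7.3% | 1.0% |
| 40 points | 0.5 | 0.20 | 0.89 | 14.5% | 2.8% |
| 40 points | 0.8 | 0.32 | 1.43 | 29.9% | 8.4% |

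**Scale.** The detectable difference at n = 40 and 80% power is (1.960 + 0.842) × 0.2236 = 0.63 SD at alpha 0.05, and (2.807 + 0.842) × 0.2236 = 0.82 SD at 0.005. A bias of 0.20 SD is 32% of the first.

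**Larger groups do not help.** Section 6.0 gives 275 subjects, which is 55 per group if equal. The bias is unchanged and the SE falls, so the 0.20 SD case rises from 14.5% to 18.2% at alpha 0.05.

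**Chance imbalance is not the issue.** At a 50% share and n = 40, shares differ by chance within ±1.96 × √(2 × 0.25/40) = ±22 points. The standard error already covers that. The table applies to a systematic difference only.

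**Effect of a diabetes term.** In 4,000 simulated trials with shares of 70% and 30%, an effect of 0.5 SD, no group effect and n = 40, the unadjusted contrast was biased by 0.20 SD and rejected about 14% of the time at alpha 0.05. With a diabetes term the bias was about 0.00 and the rate 4.9%.

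**Cost of adjusting.** Variance inflation = 1/(1 − φ²), where φ is the correlation of group with diabetes. Shares of 60/40 give φ² = 0.04 and inflation 1.042; shares of 70/30 give φ² = 0.16 and 1.190. The detectable difference becomes 0.63 × √1.042 = 0.64 SD and 0.63 × √1.190, about 0.68 SD, at alpha 0.05 (0.83 and 0.89 SD at 0.005).

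**The case against.** The size is wholly assumed. At the low end of the range the error rates are essentially nominal, and at the adjusted level they stay below 3% unless both assumptions are near their upper ends. Direction is open too: endocrinology recruitment could raise Group 3's diabetes share, and hypertension-only entrants could lower it. All of this stands.

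The design also offers partial checks. Group 3 vs 4 compares people of the same age without transplant, which gives a view of the diabetes and hypertension effect, diluted by whatever share of Group 3 is diabetic. Group 4 vs 5 is an age contrast free of diabetes, but outside transplant. A reader might infer that the trial has no means of telling diabetes from transplant or age. The documents do not support that: these contrasts help to gauge the size, although they do not remove the confounding from Group 1 vs 3 or 1 vs 2.

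Finally, this is a non-randomised mechanistic study that sets out to characterise and explore, and restricting the cause of renal failure was a deliberate step against heterogeneity. That is fair, but the restriction narrows the causes to two without fixing their proportions.

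Adjustment has limits as well. Admitting both strata does not ensure that both are enrolled, least of all in Group 2. HbA1c is measured at least a year after transplant in recipients, so adjusting Group 1 vs 3 for it could remove part of the transplant effect. Contrasts within DM2 strata are weak: with 20 per cell the detectable difference is 2.802 × √(2/20) = 0.89 SD at alpha 0.05 and 3.649 × √(2/20) = 1.15 SD at 0.005.

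**Conclusion.** The gap is real: eligibility, recruitment and model all leave diabetes uncontrolled in the two contrasts that Specific Aim 1 uses to separate age from transplant. The supported conclusion is that these contrasts can be confounded, not that they are. If the shares are similar or the diabetes effect is small, the consequence is negligible. Under the assumptions above, the bias is 0.04 to 0.32 SD.

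Two stronger readings should be resisted. A reader might take the 30% as the trial's false-positive rate. It needs a 40-point share difference, a 0.8 SD effect and no multiplicity adjustment together, and no document supplies the first two. A reader might also conclude that Group 3 fails in both contrasts, but it is the comparator for transplant only. This is a worthwhile low-cost improvement rather than a fatal flaw.

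**What to change.** - **Record** DM2 yes/no in Groups 1-3 from the chart review already used for eligibility. In Groups 1 and 2 use diabetes that predates the transplant, so that the covariate is not itself a consequence of transplant. Cause of renal failure alone does not give this status.
- **Recruit** with a running tally so that Group 3's DM2 share approximates Group 1's.
- **Model** Aims 1 and 2 with DM2 and DM2-by-time as fixed effects for the Group 1 vs 3 and Group 1 vs 2 contrasts, and report the unadjusted contrasts beside them. Make this conditional on both strata being populated in the groups compared. Groups 4 and 5 exclude DM2 and need no such term.
- **Limit** results by DM2 stratum to description, and do not adjust Group 1 vs 3 for post-transplant HbA1c.

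Cost: one added data item, a tally, a sentence or two in section 12.0, possibly slower Group 3 recruitment, and the small loss of precision shown above. The tally matters most before enrolment, because poor overlap in diabetes status cannot be repaired in the analysis.

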The inclusion/exclusion criteria will be determined by chart review and pregnancy test for females of child bearing potential.

We will not restrict volunteers with respect to gender, ethnic, or racial group.

Group 5: Healthy Control 35-45 yr old

Inclusion Criteria

35-45 years old without DM2. May have high blood pressure (systolic>140 and/or diastolic>90) as long as it is well controlled (systolic<140 and/or diastolic <90) and has not affected kidney function.

Willingness to be tested for HIV, HBV and HCV and filling out a medical questionnaire that will include diabetes screening.

We will not restrict volunteers with respect to gender, ethnic, or racial group.

Exclusion Criteria

6. Medications that are known to affect immune function (chemotherapy, anti-TNF α agents).

The inclusion/exclusion criteria will be determined by chart review and pregnancy test for females of child bearing potential.

Diversity: we will attempt to mimic the local renal transplant recipient population consisting of a disproportionately high number of males (>60%) of African-American decent, \pm 50%. This gender and race pattern of distribution is consistent with the patient population of the Ralph H. Johnson VA Medical Center outpatient clinics, where we will be recruiting most of our control populations (Groups 3-5). We therefore anticipate a diverse population as a result of eligibility at the recruitment sites.

Children will NOT be included in this study as this study is uniquely aimed at defining the immune response to PCV13 in ADULTS. The immune response to PCV13 is age-dependent and therefore completely different in children, as is the recommended vaccine frequency.

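### The blood-pressure rule for the two healthy control groups is met by either limb alone, so as worded it does not exclude uncontrolled hypertension; the Group 3 GFR criterion also needs one consistent unit

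*Combined protocol and SAP*

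**What the plan says.** **Groups 4 and 5, blood pressure.** The inclusion lists in Section 5.0 use the same rule for both healthy groups. The allowance opens with "May have high blood pressure (systolic>140 and/or diastolic>90", and its condition is "as long as it is well controlled (systolic<140 and/or diastolic <90) and has not affected kidney function". The Group 5 list repeats it: "35-45 years old without DM2. May have high blood pressure (systolic>140 and/or diastolic>90) as long as it is well controlled (systolic<140 and/or diastolic <90".

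**Group 3, kidney function.** The population description in Section 5.0 says candidates "will be screened for normal (Glomerular filtration rate \geq 60) versus abnormal (GFR $<$ 60", with no unit. The Group 3 inclusion list states the criterion as "normal kidney function” defined as glomerular filtration rate (GFR) of 60% or above".

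**Groups 4 and 5, kidney function.** The population description covers every member of these groups, hypertensive or not: "Group 4: 65-75 years old without DM2 or renal impairment" and "Group 5: Healthy persons 35-45 years of age without DM or renal impairment". Their inclusion lists mention the kidney only within the blood-pressure sentence, and neither place gives a GFR value.

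**Role of these groups.** Under Specific Aim 1 (Section 1.0), Group 3 serves to separate out the transplant component, and the healthy groups are the age-appropriate reference.

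**The concern.** A definition of high pressure properly uses *or*: either limb raised is enough. Its opposite, controlled pressure, needs both limbs below their limits. The protocol uses *and/or* in both brackets, so the two definitions overlap and one reading can satisfy both. A screener who follows the text can enrol someone with markedly raised systolic or diastolic pressure as a healthy control.

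What is at stake is how cleanly the reference groups are defined. The Section 12.0 model has fixed effects for group and time and no blood-pressure term. Blood pressure is also absent from the list of data to be collected in Section 10.0, so a control admitted under the loose reading could not be picked out later from the listed data. Recruitment runs at two institutions and eligibility rests largely on chart review, so two screeners could apply the same sentence differently.

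The Group 3 issue is smaller. Normal kidney function is the property that makes Group 3 a useful comparator, and its operative criterion is written in a form that does not match the description given shortly before it.

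**Working it through.** The plan has no figure to reproduce here. The check is one of logic, using only the cut-offs in the Group 4 and Group 5 inclusion lists (S = systolic, D = diastolic).

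**Step 1. Definitions.**
- High: S > 140 or D > 90.
- Well controlled, as written: S < 140 or D < 90.
- Well controlled, with *and*: S < 140 and D < 90.

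**Step 2. Example readings.**

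| Reading | High | Controlled as written | Controlled with *and* |
|---|---|---|---|
| 180/85 | yes | yes (85 < 90) | no |
| 135/105 | yes | yes (135 < 140) | no |
| 200/89 | yes | yes (89 < 90) | no |
| 130/80 | no | yes | yes |
| 150/95 | yes | no | no |
| 140/85 | no | yes (85 < 90) | no |
| 140/90 | no | no | no |

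As written, a reading fails only if S ≥ 140 and D ≥ 90 together.

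**Step 3. Size of the overlap.** Take all whole-number readings with S from 100 to 220, D from 50 to 120, and S > D.
- Total: 121 × 71 = 8591, less the 231 pairs with S ≤ D (1 + 2 + … + 21, for D = 100 to 120), gives 8360.
- High and controlled through diastolic alone (S 141–220, D 50–89): 80 × 40 = 3200.
- High and controlled through systolic alone (S 100–139, D 91–120, S > D): 9 × 40 = 360 for D = 91–99, plus 39 + 38 + … + 19 = 609 for D = 100–120, giving 969.
- Both high and controlled as written: 3200 + 969 = 4169 of 8360.
- Both high and controlled with *and*: 0 of 8360.

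These are counts of possible readings on an arbitrary grid. They show that the overlap is structural; they are not a proportion of patients.

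**Step 4. Consequence of the correction.** With *and*, no single reading can be both high and controlled. The sentence then makes sense only if high refers to a history or diagnosis and controlled refers to the screening reading. Values exactly on a cut-off (140/85, 140/90) meet neither definition under *and*.

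**Step 5. Group 3 kidney criterion, side by side.** Population description: at or above 60 is normal and below 60 is abnormal, with no unit. Inclusion list: 60 with a percent sign. The number is the same and the expression is not. Neither place says what the percentage would be taken of, and neither gives a measurement unit.

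**Step 6. Groups 4 and 5 kidney criterion, side by side.** The population description bars renal impairment for everyone in these groups. The inclusion lists repeat a kidney condition only for people with high blood pressure. The bar therefore exists; it is not restated in the lists and has no number there.

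**The case against.** **Staff will read it sensibly.** The words *well controlled* govern the bracket, and a clinician would probably not call 180/85 well controlled. That is fair, and it may limit the effect in practice. But the bracket is the protocol's definition of those words, and as written it admits the reading. A rule that works only when its definition is set aside should be corrected.

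**No effect is shown.** The documents give no blood-pressure distribution for the candidate controls and no link from blood pressure to antibody, OPA or B-cell outcomes. This stands in full: dilution of the group contrasts is a possibility that cannot be sized.

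**The correction leaves hypertension in the reference groups.** It does, by design, because controlled hypertension is allowed. A person aged 65–75 with controlled hypertension, no DM2, GFR at or above 60 and PPV23 more than a year ago can still fit both Group 3 and Group 4. That is a separate matter of group assignment, which this change does not settle.

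**Two stronger readings are tempting and should not be drawn.** First, a reader might take the percent sign to mean a materially different Group 3 threshold. To size such a difference one must supply a reference GFR that appears nowhere in the documents, and disregard the same number 60 in the population description. A unit slip is the more natural explanation. Second, a reader might infer that people with reduced GFR can enter Groups 4 and 5 as written, because the lists carry no GFR value and the only numeric laboratory limit common to all groups is three times the upper limit of normal. The population description sits in the same section on eligibility, bars renal impairment for all of Groups 4 and 5, and in the Group 3 entry just above calls GFR below 60 abnormal. Section 10.0 also requires a metabolic profile for all groups when no recent one exists. What is missing is a numeric restatement of a bar that already exists.

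**Conclusion.** The blood-pressure point holds. In both healthy control groups, *well controlled* is defined so that either limb suffices, and readings such as 180/85 or 135/105 are both high and well controlled. The conclusion rests only on the literal text and the protocol's own cut-offs. Its practical size is unknown, because the documents do not allow an estimate of how many controls would be admitted this way or of any shift in the immune outcomes. The sample-size and power statements in Section 12.0 are unaffected.

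The Group 3 point holds as a unit inconsistency in an operative criterion, most likely a slip, and the two statements must be reconciled. For Groups 4 and 5, restating the renal-impairment bar in the inclusion lists would be a clarification only.

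**What to change.** 1. In the Group 4 and Group 5 inclusion lists, change *and/or* to *and* in the *well controlled* bracket, keeping the protocol's cut-offs. In the same edit, say that high blood pressure means a history or diagnosis and that control is judged on the screening reading, and state on which side values exactly at a cut-off fall.
2. Reconcile the two Group 3 kidney statements in Section 5.0 to one GFR value with its unit.
3. Optionally, repeat the existing renal-impairment bar in the Group 4 and Group 5 inclusion lists so that it visibly applies to everyone and not only to those with high blood pressure.

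The cost is a few words in one section. The downside is that a few otherwise eligible controls may be screened out; the documents do not allow that number to be estimated.
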